#### 6.3.3 Cohort Closure

The Sponsor (or designee) will be in communication with the sites when the target total enrollment for a cohort has been attained. Once recruitment to a cohort is completed, accrual to the cohort will be closed, and sites will be so notified in writing. Cohorts will remain closed to further accrual, unless a decision is later made by the Sponsor (or designee) to further expand that cohort, based on protocol-defined criteria.

# 6.4. Requirements for Patient Observation

Patients will be treated on an outpatient basis, and will be evaluated and discharged from the clinic on days of scheduled study visits\*, unless hospitalization is required for other reasons or to assure patient safety.

AVID100 must be administered under close supervision in an environment where full resuscitation facilities are immediately available. IV infusions will be carefully monitored to assess safety and tolerability by qualified site medical personnel. Such personnel must be available in order to evaluate and treat any AEs, as well as to evaluate whether continued participation of the patient in the study is warranted or advisable.

- Phase 1a Dose-Escalation Cohorts: Patients will be carefully observed for a minimum of 4 hours following completion of the first administration of study drug (Day 1) for evidence of any treatment-related AE(s), and so that final Day 1 samples for post-dosing PK assessments may be obtained\*\*, and a minimum of 1 hour following completion of subsequent infusions.
- Phase 2a Expansion Cohorts: Patients will be carefully observed for a minimum of 2 hours following completion of the first administration of study drug (Day 1) for evidence of any treatment-related AE(s) \*\*, and a minimum of 1 hour following completion of subsequent infusions. *PK samples will only be collected prior to dosing on Day 1 of each cycle in the Dose Expansion Cohorts.*

At the end of each infusion, the IV line must remain in place for at least 1 hour to allow administration of IV drugs, if necessary.

Patients will be followed on an outpatient basis during the interval between each scheduled study visit.

\*Clinical and laboratory assessments will occur at the frequencies indicated (see **Section 7**; Study Assessments). In the event of an AE, assessment frequencies may be increased, as clinically indicated.

\*\*Comprehensive collection of clinical samples is critical to the conduct of this study. In situations where collection of 4h samples is logistically difficult due to clinic staff availability, the observation period may be shortened, and an "end of day" sample may be obtained at the latest practical time. Such an option is available ONLY after previous discussion with and approval by the Sponsor.

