# 6.5. **Drug Treatment Regimen**

### 6.5.1 Study Start Day

All patients will receive the initial dose of study drug on Day 1 of Cycle 1 (C1/D1).

On the day of the first scheduled study drug infusion, and prior to the start of infusion (SOI), the Investigator must assess whether any changes have occurred in the clinical state of the patient since Screening, which would exclude the patient from the trial.

# 6.5.2 Patient Availability During Cycle 1

The site should calculate study assessment days as well as sample collection dates and times in advance of scheduling a patient's first day of study drug administration, so as to plan accordingly to avoid assessment or collection requirements during non-routine times such as weekends, holidays, etc.

Given the schedule of study drug administration outlined herein, and the PK sampling schedule (see **Section 7.5**; Pharmacokinetic Assessments), patients must be available:

- Phase 1a: on Days 1, 2, 4 (± 1 day), and 8 of Cycle 1, therefore, consideration should be given to scheduling Day 1 on a Monday or Tuesday\*
- Phase 2a: on Days 1, 4 (± 1 day), and 8 of Cycle 1, therefore consideration should be given to scheduling Day 1 on a Monday, Tuesday, or Friday\*

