### Phase 2a Expansion Cohorts

- Cycle 1 and Cycle 5
  - o Day 1
    - Prior to SOI
    - EOI (± 5 min)
  - o Day 8
    - At time of visit
- Each other cycle
  - o Day 1
    - Prior to SOI
- EOT
- 1M FUP
- As clinically indicated in the event of an IRR

\*Comprehensive collection of clinical samples is critical to the conduct of this study. In situations where collection of a 4h after EOI sample is logistically difficult due to clinic staff availability, the observation period may be shortened, and an "end of day" sample may be obtained at the latest practical time. Such an option is available ONLY after previous discussion with and approval by the Sponsor.

Note: Whole blood (~ 5 mL) to be collected in serum acquisition tubes at each of the indicated timepoints. In the event that a collected serum sample is inadequate or insufficient for PK analysis, the analysis of PK can be done using an anti-drug antibody (ADA) serum sample from the same time point, if available.

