Phase 1a only: Tumor Marker Measurement 	x							х			x	x b		q3m for 1y, q6m after c	
Imaging for Disease (and Pulmonary Status) 	х							х			х	x b		q3m for 1y, q6m after c q3m for 1y,	
Response Assessment 								X			x	x b		q5m for fy, q6m after c	
ADDITIONAL ASSESSMENTS															
Phase 1a: PK Sampling 		SOI; EOI; 2, 4h after EOI	24h after EOI	х	x	SOI EOI	х		SOI EOI			х	х		xe
Phase 2a: PK Sampling 		SOI EOI			х	SOI			SOI, EOI-C5 only	C5 only		х	х		xe
Phase 1a: Archival Tumor for EGFR confirmation and biomarker studies 		optional; subm enrollme			r study										
Phase 2a: Tumor for exploratory studies 	required														

Phase 2a: Blood for Exploratory Studies 		x									х		
TRIAL TREATMENT													
AVID100 Infusion (2-h)		X				X			X				
Phase 1a: Post-Infusion Monitoring		4h				X			X				
Phase 2a: Post-Infusion Monitoring		2h				X			X				

\*Given the Q3W dosing frequency, EOT and 1M FUP evaluations may be combined in those situations where scheduling coincides, provided a minimum of 30 days of post-dosing follow-up have been observed.

Abbreviations: SOI-start of infusion; EOI-end of infusion; EOT-end of treatment; 1M FUP-1 month follow-up

- a Need not be assessed prior to Cycle 1 if  $\leq$  7 days since screening;
- b Conduct only if > 6 weeks since the previous assessment;
- c To be conducted in the event of ongoing objective response (OR) or stable disease (SD) at the end of treatment; continue until progressive disease (PD) or another therapeutic intervention is initiated d End of Cycle assessments may be conducted at any time during the week prior to Day 1 of the next cycle.
- e Additional ADA and PK sampling to be performed in the event of an IRR, as close as possible to the onset of the event
- 1. Informed Consent: To be signed prior to enrollment and prior to performing any protocol-related procedure, unless such testing was performed previously as part of the routine clinical management of the patient.

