TABLE 8: PHARMACOKINETIC SAMPLING SCHEDULE See also TABLE 4													
Study Day	Phase 1a	Phase 2a	Allowance (+/-)	Reference									
CYCLE 1													
Day 1	SOI	SOI		Prior to SOI									
	EOI	EOI	5 min										
	2h		15 min	EOI									
	4h		15 min										
Day 2	24h		1h										
Day 4	At time of visit		1 day										
Day 8	At time of visit	At time of visit											
CYCLE 2													
Day 1	SOI	SOI		Prior to SOI									
	EOI		5 min	EOI									
Day 8	At time of visit												
POST-TREATMENT													
EOT	At time of visit	At time of visit											
1M FUP	At time of visit	At time of visit											
In the event of an IRR	At time of	At time of											
In the event of an IRR	event	event											
TOTAL SAMPLES	12	5											

SOI = Start of Infusion EOI = End of Infusion

PK samples for each additional cycle:

• Phase 1a: Day 1 (SOI, EOI)

• Phase 2a: Day 1 (SOI)

Day 1 (SOI, EOI) *Cycle 5 only*Day 8 (at time of visit) *Cycle 5 only* 

Actual collection times are to be recorded on the patient's eCRF or other equivalent sample collection log as authorized by the Sponsor (or designee).

Comprehensive collection of clinical samples is critical to the conduct of this study. In situations where collection of the 4h sample is logistically difficult due to clinic staff availability, an "end of day" sample may be obtained at the latest practical time. Such an option is available ONLY after previous discussion with and approval by the Sponsor.

	TABLE 9: MAXIMUM TOTAL BLOOD COLLECTION VOLUMES											
STUDY	Vol./	Screen	ing	Cycl	e 1	Cycle	2	EO	Γ	1M F	UP	TOTAL
ASSESSMENTS	sample (mL)	# of Samples	Vol. (mL)	VOLUME								
Phase 1a												
Hematology	5	1	5	3	15	2	10	1	5	1	5	40
Chemistries	10	1	10	3	30	2	20	1	10	1	10	80
Coagulation	5	1	5	3	15	2	10	1	5	1	5	40
Pregnancy Test	5	1	5	0		0		0		0		5
ADA Testing	5	0		1	5	1	5	1	5	1	5	20
Tumor Markers	5	1	5	0		1 (end)	5	1	5	1	5	20
PK Studies	5	0		7	35	3	15	1	5	1	5	60
Total Volume			30		100		65		35		35	265
Phase 2a												
Hematology	5	1	5	3	15	2	10	1	5	1	5	40
Chemistries	10	1	10	3	30	2	20	1	10	1	10	80
Coagulation	5	1	5	3	15	2	10	1	5	1	5	40
Pregnancy Test	5	1	5	0		0		0		0		5
ADA Testing	5	0		1	5	1	5	1	5	1	5	20
PK Studies	5	0		3	15	1	5	1	5	1	5	30
Exploratory Studies	20	1	20	0		0		1	20	0		40
Total Volume	•		45		80		50		50		30	255

Along with Screening, single days not detailed with maximum blood volume requirements > 20 mL:

- Phase 1a: Cycle 1/Day 1= 50mL, Day 4=25mL

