- Phase 2a: Cycle 1/Day 1=35mL (55 mL if biomarker sample is drawn prior to dosing on C1/D1)

Blood volumes for each additional cycle: 50 mL, 60 mL for Cycle 5

If sites are able to perform hematology, serum chemistry, and coagulation studies with smaller volumes of blood per sample, they are encouraged to do so. Required PK, and ADA volumes are fixed and should not be reduced.

For the purpose of estimating a patient's total blood collection volume during study participation, maximum estimates are used. During a patient's study participation, the maximum amounts of venous blood that will be collected are listed above. Study duration is based on 6 weeks estimated average patient participation, i.e., an average of Cycle 1 (3 weeks) plus Cycle 2 (3 weeks).

An indwelling venous access device is required for PK blood sample collections on Day 1 of Cycle 1. When an indwelling catheter (or equivalent venous access) is utilized, a blood flush discard of up to 3 mL is to be done before drawing the first blood tube collected on the scheduled day/time for routine laboratory tests and PK samples. **Blood flush discard volumes ARE NOT included in volume calculations in table above and should be considered when summarizing actual blood collection volumes.** 

Given the Q3W dosing frequency, EOT and 1M FUP evaluations may be combined in those situations where scheduling coincides, provided a minimum of 30 days of post-dosing follow-up have been observed.

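### Section 6.4 limits Phase 2a PK sampling to pre-dose Day 1 draws, contradicting Section 7.5.1 and Tables 7 to 9, which also schedule end-of-infusion, Day 8 and follow-up samples

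*Combined protocol and SAP*

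**What the plan says.** Section 6.4, within the bullet on how long Phase 2a patients are observed after infusion, states: "PK samples will only be collected prior to dosing on Day 1 of each cycle in the Dose Expansion Cohorts".

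The other places that deal with Phase 2a PK sampling say something different:

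- **Section 7.5.1**, under "Cycle 1 and Cycle 5", lists a pre-dose sample and an end-of-infusion (EOI) sample on Day 1 and a sample on Day 8. Every other cycle has one pre-dose sample. Further samples are due at EOT, at the 1-month follow-up and in the event of an infusion-related reaction (IRR).
- **Table 7** shows pre-dose and EOI samples on Cycle 1 Day 1 and a sample on Day 8. For later cycles it shows "SOI, EOI-C5 only" on Day 1 and Day 8 in Cycle 5 only. EOT, 1-month follow-up and IRR samples are marked.
- **Table 8** has the same schedule and closes with "TOTAL SAMPLES 12 5" (Phase 1a, then Phase 2a).
- **Table 9** counts 3 PK samples in Phase 2a Cycle 1 and one each in Cycle 2, at EOT and at the 1-month follow-up, for 30 mL in all. The notes under it add: "Blood volumes for each additional cycle: 50 mL, 60 mL for Cycle 5".
- **Section 6.5.2** cites the PK schedule in Section 7.5 and requires attendance "Phase 2a: on Days 1, 4 (± 1 day), and 8 of Cycle 1".

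Further PK characterization is the only secondary objective of Phase 2a (Section 3.2.2).

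**The concern.** The 6.4 sentence is specific, uses the word only, and sits in the instructions that staff follow on the infusion day. A site that relies on it would stop PK sampling once the infusion starts. Section 7.5 says that no additional samples may be collected without a formal amendment, which gives such a site a further reason not to draw at end of infusion.

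The EOI sample has a window of ± 5 minutes, so a missed one cannot be recovered. Pre-dose samples alone give a baseline and later troughs. These support Cmin but give no observed peak. Section 14.3.1 includes the expansion cohorts in the PK analysis only for patients with enough concentrations for the calculation, so lost samples could also remove patients from that analysis.

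**Working it through.** No formula is needed beyond counting scheduled samples. IRR samples are left out because they depend on an event, and EOT and the 1-month follow-up are counted as separate visits.

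**1. Reproduce the Table 8 totals.**

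- Phase 1a: Cycle 1 has 7 (pre-dose, EOI, 2 h, 4 h, Day 2, Day 4, Day 8), Cycle 2 has 3, EOT 1, follow-up 1. 7 + 3 + 1 + 1 = 12, as printed.
- Phase 2a, counted the same way: Cycle 1 has 3 (pre-dose, EOI, Day 8), Cycle 2 has 1, EOT 1, follow-up 1. 3 + 1 + 1 + 1 = 6, but 5 is printed.
- Combining EOT with the follow-up visit would give 5 for Phase 2a, but the same step would give 11 for Phase 1a, which does not match the printed 12.

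**2. Check which schedule the blood volumes assume (Table 9, Phase 2a, 5 mL per PK sample).** One set of hematology, chemistry and coagulation takes 5 + 10 + 5 = 20 mL, and an ADA sample takes 5 mL.

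- PK total: 6 × 5 = 30 mL, as printed.
- Cycle 1: 3 × 20 + 5 + 3 × 5 = 80 mL, as printed. With one PK sample, as under 6.4, it would be 70 mL.
- Cycle 1 Day 1: 20 + 5 + 2 × 5 = 35 mL, as printed, so two PK draws are budgeted on that day. Under 6.4 it would be 30 mL.
- Cycle 5: 2 × 20 + 5 + 3 × 5 = 60 mL, as printed, against 2 × 20 + 5 + 5 = 50 mL for a cycle with one PK sample. The extra 10 mL is the EOI and Day 8 samples.

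The volumes therefore follow 7.5.1, not 6.4.

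**3. Count what each reading of 6.4 keeps.**

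| Samples per Phase 2a patient | Through Cycle 2 | Through Cycle 5 |
|---|---|---|
| Pre-dose | 2 | 5 |
| EOI | 1 | 2 |
| Day 8 | 1 | 2 |
| EOT | 1 | 1 |
| 1-month follow-up | 1 | 1 |
| **Scheduled in 7.5.1** | **6** | **11** |
| Kept if 6.4 is read literally (pre-dose only) | 2 | 5 |
| Kept if 6.4 governs Day 1 draws only (EOI dropped) | 6 − 1 = 5 | 11 − 2 = 9 |

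The literal reading loses 6 − 2 = 4 samples through Cycle 2 and 11 − 5 = 6 through Cycle 5. The narrower reading loses 1 and 2. Neither reading keeps any EOI sample.

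**The case against.** The best defense is that Section 6.4 governs observation after infusion and is not the sampling schedule. Its footnote on study visits refers clinical and laboratory assessments to Section 7. Section 6.5.2 tells sites to plan sample dates from Section 7.5 and requires attendance on Day 8 of Cycle 1. Section 7.5.1 and Tables 7 to 9 agree on which samples are to be drawn. A site working from the schedule would collect everything. This stands, and it makes the loss conditional. It does not remove the conflict: that footnote is not attached to the PK sentence, and a site that reads both places still cannot comply with both.

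A second defense is that the sentence contrasts with the Phase 1a bullet, where patients stay 4 hours partly so that the last Day 1 samples can be drawn. Read that way it restricts Day 1 only and leaves Day 8 intact. This is a fair reading, but the EOI sample is itself a Day 1 draw and is excluded all the same.

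A reader might infer that following 6.4 necessarily costs every peak and mid-cycle sample, and that a Phase 2a requirement for Cmax, Tmax and AUC therefore fails. The documents do not support that. The loss of Day 8 depends on the literal reading. Section 14.3.3.2 is a parameter list for the whole trial, and it includes Cmin, which troughs support. Section 3.3 says that Phase 2a PK is meant to be less extensive than in Phase 1a. Even under 7.5.1, one post-dose sample on Day 1 means that the schedule largely fixes Tmax and that AUC rests on few points.

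The Table 8 total is a clerical slip. The rows are clear, and nothing in the documents uses the total to decide which samples are drawn.

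**Conclusion.** The contradiction is real, and it is an internal inconsistency rather than a choice of design. The intended Phase 2a schedule is clear from 7.5.1 and Tables 7 to 9, and one sentence in 6.4 does not match it.

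The firm part is the end-of-infusion sample: 6.4 excludes it on any reading, at a cost of two samples per patient through Cycle 5 and any observed peak. The wider loss, down to 2 of 6 samples through Cycle 2 and 5 of 11 through Cycle 5, with Day 8, EOT, 1-month follow-up and IRR samples also gone, applies only if the sentence is read literally.

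These counts assume that the patient starts every cycle counted, that EOT and follow-up are separate visits, and that the site acts on 6.4 alone. The documents do not say whether any sample has been missed, so this is a risk to the Phase 2a secondary objective and not a demonstrated failure of it.

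**What to change.** Replace the PK sentence in Section 6.4 with a reference to the Phase 2a schedule in Section 7.5.1 and Table 8, so that the sampling rule is stated in one place. As a minor accompanying correction, change the Table 8 Phase 2a total from 5 to 6 so that it agrees with its own rows and with the 30 mL in Table 9.

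The cost is one sentence and one table cell. No visit, sample or blood volume is added to what 7.5.1 and Table 9 already provide for.

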# 6.5. **Drug Treatment Regimen**

### 6.5.1 Study Start Day

All patients will receive the initial dose of study drug on Day 1 of Cycle 1 (C1/D1).

On the day of the first scheduled study drug infusion, and prior to the start of infusion (SOI), the Investigator must assess whether any changes have occurred in the clinical state of the patient since Screening, which would exclude the patient from the trial.

# 6.5.2 Patient Availability During Cycle 1

The site should calculate study assessment days as well as sample collection dates and times in advance of scheduling a patient's first day of study drug administration, so as to plan accordingly to avoid assessment or collection requirements during non-routine times such as weekends, holidays, etc.

Given the schedule of study drug administration outlined herein, and the PK sampling schedule (see **Section 7.5**; Pharmacokinetic Assessments), patients must be available:

- Phase 1a: on Days 1, 2, 4 (± 1 day), and 8 of Cycle 1, therefore, consideration should be given to scheduling Day 1 on a Monday or Tuesday\*
- Phase 2a: on Days 1, 4 (± 1 day), and 8 of Cycle 1, therefore consideration should be given to scheduling Day 1 on a Monday, Tuesday, or Friday\*

# 6.5.3 Therapy with AVID100

Based on their cohort assignment patients will receive the assigned dose of study drug as described below, by the route and schedule as described below:

#### 6.5.3.1. Doses to be Administered

#### 6.5.3.1.1. Doses to be Evaluated During Phase 1a

Dose cohorts will be numbered sequentially (i.e., Cohort 1, Cohort 2, etc.). The number of cohorts evaluated and the MAD will depend upon toxicities experienced during Cycle 1.

The initial dose of AVID100 to be evaluated is calculated based on the highest non-severely toxic dose (HNSTD) observed in nonclinical toxicology studies, and will be **20 mg/m²/**dose

\*unless the study site has weekend hours of operation

(with the maximum dose to be administered in this trial not to exceed **330 mg/m²/dose).** An accelerated titration design (1 patient per cohort) will be used for dose-escalation for up to 2 cohorts or until the occurrence of an event that activates a stopping rule. Thereafter, dose-escalation will follow a standard 3+3 design with a target toxicity level of 33.3% or less as determined by DLTs. Doses will be calculated as follows:

- Dose Part A: Up to 2 cohorts (until at most Cohort 3) will receive consecutive 100% increases in dose (EXAMPLE: Cohort 1 = 20 mg/m²/dose, Cohort 2 = 40 mg/m²/dose, etc.) until the occurrence of:
  - A study drug-associated 
     Grade 2 toxicity or accrual to Cohort 3, whichever occurs first (Part B will commence)
  - o A study drug-associated DLT (Part C will commence)
- **Dose Part B**: Cohorts will receive consecutive 50% increases in dose (EXAMPLE: Cohort  $x = 60 \text{ mg/m}^2/\text{dose}$ , Cohort  $x+1 = 90 \text{ mg/m}^2/\text{dose}$ , etc.) until the occurrence of:
  - o A study drug-associated DLT (Part C will commence)
  - > 1 patient with a study drug-associated DLT (dose escalation will stop)
- **Dose Part C**: Cohorts will receive consecutive 25% increases in dose (EXAMPLE: Cohort  $x = 60 \text{ mg/m}^2/\text{dose}$ , Cohort  $x+1 = 75 \text{ mg/m}^2/\text{dose}$ , etc.) until the occurrence of:
  - > 1 patient with a study drug-associated DLT (dose escalation will stop)

Note: The Investigator(s) and Sponsor's Medical Monitor(s) will review clinical and laboratory safety data on an ongoing basis throughout the study and make decisions regarding the advisability of continuing accrual to a particular dose cohort, and/or escalating the dose and allowing accrual to a higher dose cohort.

Based on emerging tolerability data the Sponsor may choose to escalate the dose between cohorts at an increment less than the percent increase allowed above in an effort to protect patient safety.

#### 6.5.3.1.2. Dose to be Administered During Phase 2a

Patients entered to the Phase 2a portion of this study will receive study drug at the RP2D established during the Phase 1a portion of the study. The MTD and RP2D has been determined to be 220 mg/m^2.

Ongoing safety evaluations will continue during accrual of patients to the Phase 2a expansion cohorts to determine whether any newly identified AEs necessitate modifications to the protocol or discontinuation of accrual to patients within any cohort (Section 6.6.3.3).

#### 6.5.3.1.3. Changes in Dose to be Administered

In both Phase 1a and Phase 2a, once assigned to a dose cohort each patient will continue to be treated with study drug at that same dose level throughout the duration of their time on study, unless dose reduction is necessary due to the occurrence of a DLT or other toxicity warranting dose reduction at the Investigator's discretion. There will be no intra-patient dose-escalation.

Dose adjustments should be made in the event of noted weight change ( $\pm$  10%, less at the site's discretion or if required by institution procedures) at visits that require weight measurement.

#### 6.5.3.2. Route of Administration

Study drug will be administered by the IV route, via indwelling venous access catheter, utilizing a controlled infusion device. Infusion sets must be made of DEHP-free material and must contain an in-line filter (0.22 micron pore size). Flexible containers of NS should be made of polyvinyl chloride.

The catheter may be placed into a peripheral vein (if accessible); administration via central venous catheter or port (if in place) is allowed.

In those instances when study drug administration is associated with PK sampling, and administration is via peripheral IV catheter, infusions will be delivered into the arm contralateral to that from which blood samples for PK analysis are being obtained.

